# 7. Response Measures and Summary of Data Collection Methods

#### 7.1 Effectiveness Measures

# 7.1.1 Primary Effectiveness Measure

The primary effectiveness measure is the EI assessment of loss of jawline definition using the ALJDS. Each side of the jawline (left and right) will be assessed independently.

# 7.1.2 Secondary Effectiveness Measures

Secondary effectiveness measures include independent, noncollaborative assessments by both the EI and the subject of global aesthetic improvement in jawline area using the 5-point GAIS (Table 6) and subject responses on the validated FACE-Q Satisfaction with Lower Face and Jawline questionnaire. For GAIS and FACE-Q questionnaires, 1 overall assessment will be provided to encompass both sides.

Table 6 5-Point Global Aesthetic Improvement Scale

Score	Grade	
2	Much Improved	
1	Improved	
0	No Change	
-1	Worse	
-2	Much Worse	

### 7.1.3 Other Effectiveness Measures

Other effectiveness measures include:

### **7.2** Safety Measures

Safety measures include:

- Subject assessment of procedural pain during treatment on an 11-point scale ranging from 0 (no pain) to 10 (worst pain imaginable)
- Subject assessment of jaw function using the 20-item Jaw Functional Limitation Scale questionnaire
- Presence, severity (mild, moderate, or severe), and days with ISRs recorded by subjects in daily safety diaries for approximately 30 consecutive days after any treatment (initial, touch-up, and maintenance)
- AEs observed by the TI or reported to the TI by the subject
- Snellen visual acuity, confrontational visual fields, and ocular motility assessed by the TI (or designee)
- EIs assessment of facial sensation
- Pronunciation video recordings
- Monitoring of concomitant medications and concurrent procedures

The subject daily diary will list the following ISRs that have been reported previously with HA dermal filler injections:

- redness
- pain after injection
- tenderness to touch
- firmness
- swelling
- lumps/bumps
- bruising
- itching
- discoloration

The subject's daily safety diary will list the following severities for ISRs to be recorded:

Subjects are to bring the e-diaries to their Day 14 and Day 30/Month 1 visits for review by the TI, and the TI will determine if the ISR qualifies as an AE.

AEs will be monitored continuously throughout the study and documented on an AE eCRF.

Vital sign measurements, including blood pressure (systolic and diastolic, while subject is seated), temperature, pulse, and respiratory rate, and a urine pregnancy test for female subjects of childbearing potential will also be performed. Females who are postmenopausal for at least 1 year or who do not have a uterus at the time of study entry are considered not of childbearing potential.

# 7.3 Demographics and Baseline Characteristics

Subject demographics and baseline characteristics to be collected include sex, age, race, height, weight, Fitzpatrick skin phototype and sun exposure, smoking and tobacco history, medical/surgical/cosmetic/dental procedure history, and prior medications.

#### 7.4 Treatment Characteristics

Treatment characteristics will be evaluated by collecting information on anesthesia usage, injection volume, product moldability (11-point scale where 0 = stiff and 10 = moldable), and injection ease (11-point scale where 0 = difficult and 10 = easy).

# 7.5 Summary of Methods of Data Collection

Electronic data capture will be used to collect study-specific information, such as subject and investigator assessments. Completed eCRFs will be reviewed and attested to by the PI.

Investigators will provide access to hospital files, medical records, and other source documents containing subject clinical/medical or research study information. Source document verification will be performed by the sites' assigned monitors.

Subjects will complete the ISR diaries electronically. Sites can save photographs onto supplied electronic media and send the encrypted storage device to

Alternatively, files containing the facial digital photographs may be directly uploaded to

#### 8. Statistical Procedures

A separate statistical analysis plan will be prepared to provide specifications for all analyses. The plan will be finalized and approved prior to clinical database lock. One database lock is planned after all subjects exit the study.

Descriptive statistics will be presented for key outcome measures. Categorical variables will be summarized with frequency and relative frequency. Continuous variables will be summarized by number of subjects, mean, median, standard deviation, minimum, and maximum. Where appropriate, 2-sided 95% CIs for population mean, or population proportion, will be provided as part of the descriptive summary.

Every attempt will be made to collect complete data and limit the occurrence of missing data. Imputation of missing data may be used for sensitivity analysis of the primary effectiveness endpoint. Deviations from the analyses planned in the statistical plan will be documented in the clinical study report.

# 8.1 Analysis Populations

The following analysis populations will be used in the analyses for this study:

- Intent-to-treat (ITT) population: all randomized subjects
- Safety population: all subjects randomized to treatment group who receive at least 1 study treatment and all subjects randomized to control group

Unless specified otherwise, all effectiveness analyses will be performed on the ITT population using the "as-randomized" assignment for each subject (ie, if a subject randomized to the control group is treated inadvertently at the start of the study, the

assessments for that subject will nonetheless be included in the control group analysis). All safety analyses will be conducted using the safety population.

# 8.2 Collection/Derivation of Primary and Secondary Effectiveness Assessments

### 8.2.1 Primary Effectiveness Variable

The primary effectiveness variable is the responder rate at Month 6. A responder is defined as a subject who shows at least a 1-point improvement on the ALJDS from baseline based on EI assessment on both sides of the jaw. Baseline is defined as the last assessment by EI prior to randomization.

# 8.2.2 Secondary Effectiveness Variables

Secondary effectiveness variables include EI and subject assessed GAIS responder rates, where a "responder" is a subject who shows improvement in the overall aesthetic assessment in jawline area (Improved or Much Improved on GAIS) at the Month 6 Visit, and subject mean overall satisfaction on the validated FACE-Q Satisfaction with Lower Face questionnaire at Month 6.

# 8.3 Hypothesis and Methods of Analysis

# 8.3.1 Primary Effectiveness Analyses

The study device will be determined to be clinically effective if at least 50% of subjects in the treatment group are observed to be responders (subjects who show  $\geq$  1-point improvement on the ALJDS compared with pretreatment) at Month 6 and if the responder rate for treatment group is statistically superior to the responder rate for the control group at Month 6. The following hypotheses will be tested:

$$H_o$$
:  $P_v < 50\%$   
 $H_a$ :  $P_v \ge 50\%$ 

and

$$H_o$$
:  $P_v \notin P_c$   
 $H_a$ :  $P_v > P_c$ 

where  $P_v$  and  $P_c$  denote the responder rates for the treatment group at Month 6 after last treatment and control group at Month 6 after randomization, respectively. The first

hypothesis will be tested using 2-sided 95% CI. The null hypothesis will be rejected if the lower bound of the 95% CI is greater than or equal to 50%. The second hypothesis will be tested using 1-sided Fisher's exact test at 2.5% significance level (or 2-sided Fisher's exact test at 5% significance level) to compare responder rates between the treatment and control groups. The null hypothesis will be rejected if the 1-sided p-value is < 0.025 (or 2-sided p-value is < 0.05).

The primary effectiveness analysis will be performed on the ITT population using the last observation carried forward for any missing assessment of the primary endpoint at the Month 6 Visit. Additionally, as part of sensitivity analysis, the primary effectiveness analysis will be repeated on the ITT population using observed data as well as using multiple imputation procedure. Details of the multiple imputation procedure will be provided in the statistical analysis plan. Furthermore, additional sensitivity analyses of the primary effectiveness endpoint will be performed on the ITT population, excluding subjects who were inadvertently unblinded to the EI or who did not have a baseline ALJDS score of 2 or 3.

The impact of investigational sites on the primary effectiveness analysis at Month 6 will be evaluated by presenting the primary effectiveness analysis by each site.

[figure not shown]
# 8.3.2 Secondary Effectiveness Analyses

The following analyses will be performed for each of the secondary effectiveness endpoints:

- Responder rates with 95% CI for the treatment group based separately on the EI and subject assessments of GAIS, where a "responder" is a subject who shows improvement in the overall aesthetic assessment in jawline area (Improved or Much Improved on GAIS) at the Month 6 Visit.
- Descriptive summary of the change in overall score of subject's satisfaction with lower face and jawline since baseline at the Month 6 Visit based on the treatment group subjects' responses on the validated FACE-Q Satisfaction with Lower Face and Jawline questionnaire; a 2-sided paired t-test at the 5% level to demonstrate that the mean overall satisfaction score at Month 6 is statistically greater than that at baseline. This test is only performed if the primary endpoint is met.

No multiplicity adjustment will be made for the 2 GAIS responder rates since these endpoints are descriptive in nature.

### 8.3.3 Other Effectiveness Analyses

# 8.3.4 Safety Analyses

Subject assessment of procedural pain score and of jaw function using the 20-item Jaw Functional Limitation Scale questionnaire will be summarized descriptively. Assessments from the pronunciation recordings and facial sensation assessment will be summarized descriptively.

Snellen visual acuity, confrontational visual fields, and ocular motility assessments will be summarized descriptively.

ISRs will be summarized by maximum severity and ISR days for initial, touch-up, and maintenance treatments, separately. Summaries will include the incidence rate for each ISR.

Treatment-emergent AEs and treatment-related AEs (ie, device- or procedure-related) will be summarized by System Organ Class and Preferred Term, and severity. In addition, treatment-related AEs will also be tabulated by duration, severity, causality, action taken, and outcome. The summary will include incidence rate as well as total number of events.

AEs that occur after obtaining written IC but before treatment will be listed, but not summarized.

# 8.4 Subgroup Analyses

Details will be provided in the statistical analysis plan.

### 8.5 Sample Size Calculation

Sample size is determined to provide adequate power to demonstrate that the product is effective as well as safe. A sample size of 120 subjects in the treatment group and 40 subjects in the control group will provide > 99% power to detect a difference of at least 40% in the responder rates between the groups. This calculation is based on a 1-sided Fisher's exact test at the 2.5% level. The treatment group is assumed to have at least 80% responder rate and the control group will have at most 40% responder rate. Assuming a screen fail rate of 25% and a drop-out rate of 15% between randomization and the Month 6 visit, up to 280 subjects will be enrolled, with at least 144 subjects and at most 162 subjects randomized to the treatment group and at least 48 subjects and at most 54 subjects randomized to the control group (3:1 ratio).

This sample size is considered to be adequate to determine the safety profile of the product in the jawline area. Assuming a screen fail rate of 25%, a 5% drop-out rate between randomization and initial treatment for the treatment group, and a 15% drop-out rate between randomization and optional treatment for the control group, it is estimated that at least 176 subjects will be treated in the study. With 176 treated subjects, there is at least 92% power to detect an AE related to treatment with an incidence rate of 1.5% in the population using a 1-sided exact binomial test at the 2.5% level.

The commercial software, PASS (2008, Version 8.0.13), was used for the power calculation. The sample size calculation used an inequality test for 2 proportions to demonstrate that the treatment group is superior to the control group. The safety calculation used an inequality test for 1 proportion.

# 8.6 Interim Analyses

No interim analysis is planned. An analysis of the primary and secondary endpoints may be conducted once all subjects have passed the primary timepoint (Month 6). If such an analysis is conducted, the details of the analysis will be described *a priori* in other study documents.

#### 9. Materials

### 9.1 Study Treatment

#### 9.1.1 **Product Description**

VOLUX XC is a newly formulated sterile, biodegradable, nonpyrogenic, viscoelastic, clear, colorless, homogenized, HA gel implant (dermal filler). The HA is produced by *Streptococcus* species of bacteria and is mixed with phosphate buffer and crosslinked by adding a minimum amount of 1,4-Butanediol diglycidyl ether (BDDE) to form a 3D HA gel. The HA concentration is 25 mg/mL, and 0.3% weight by weight (w/w) lidocaine hydrochloride is added to enhance subject comfort.

#### 9.1.2 Instructions for Use and Administration

For investigational use in this study, VOLUX XC injectable gel with lidocaine will be administered via the supplied needles (27 G 1/2") or cannula (25 G 1 1/2") to the pre- and post-jowl area, chin, marionette lines, and angle of the mandible to restore jawline definition, provide a smooth contour, and achieve an aesthetically pleasing result. When making an entry point for the cannula, only use the introducer needle that is co-packaged with the provided cannula.

The TI must be experienced in the use and administration of HA implants and be practicing in the field of aesthetic medicine, plastic/cosmetic/reconstructive surgery, or dermatology. Before the study begins, the TI will receive training in the administration of VOLUX XC according to the technique specified for this study.

The TI will use aseptic injection technique and inject the treatment slowly using gentle, even pressure on the syringe. The detailed recommended injection technique is provided in the VOLUX XC IDFU included in the Site Study Binder.

Note: In Study V25L-001, a small percentage of treated subjects (3.4%, 4/119) after initial or touch-up treatment and 1.1% (1/89) after repeat treatment experienced treatment-related AEs of speech disorder (investigator term: unclear pronunciation), which were considered to be related to the physical presence of filler in subjects' chin. The events were generally mild in severity, self-limiting, and resolved without sequelae within a few days. The subjects who experienced these events tended to have larger than average volumes injected into the pogonion and mentum (> 1.5 mL in each area).

### 9.1.3 Treatment Regimen Adjustments

Up to 2 treatment sessions 30 days apart are allowed; maintenance treatment is allowed 12 months after initial (or touch-up, if performed) treatment for the treatment group subjects. The TI will determine the appropriate volume of VOLUX XC to inject at the initial and touch-up treatments based on his/her clinical experience, but the maximum volume must not exceed 8.0 mL for initial and touch-up treatments combined. Injection volume for maintenance treatment must not exceed 8.0 mL.

# 9.2 Other Study Supplies

Allergan will provide digital imaging equipment and other supplies specific to this study (eg, 27 G 1/2" needles [see Section 12.5.1] and/or 25 G 1 1/2" cannulas). The investigational site is responsible for urine pregnancy tests, routine supplies related to device administration and follow-up visits (eg, antiseptics, drapes, gloves, gauze, anesthesia, ice packs, blood pressure cuff, and internet connection for IWRS, eCRF completion, and for submitting digital images).

# 10. Study Administration Procedures

The clinical study shall not begin until the required approvals from the appropriate regulatory authorities and IRBs have been obtained.

# 10.1 Subject Entry Procedures

# **10.1.1** Overview of Entry Procedures

Prospective subjects as defined by the criteria in Sections 5.3 and 5.4 (inclusion/exclusion criteria) will be considered for entry into this study. A subject is considered to have entered the study upon signing the ICF, which occurs prior to any screening procedures.

Screening procedures (Table 1) include:

- Collection of demographic information
- Collection of height, weight, and vital signs
- Evaluation of Fitzpatrick skin phototype and history of sun exposure
- Collection of smoking and tobacco history
- Collection of medical/surgical/cosmetic/dental procedures history
- Administration of urine pregnancy test for female subjects of childbearing potential

- Evaluation of inclusion/exclusion criteria
- 3D facial digital imaging
- Evaluation by the EI of jawline definition using the ALJDS

Subjects choosing not to participate in facial digital imaging through checkbox selection on the ICF will be excluded from the study. Allergan shall have full ownership rights to any photographs derived from the study.

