# **Early Discontinuation of Subjects**

Each subject reserves the right to withdraw from the study at any time without jeopardy to his/her future medical care. Subjects who discontinue early are to complete applicable study visit procedures and Early Exit Visit procedures. Subjects may also be administratively withdrawn if they do not return for follow-up visits. For any subject who withdraws from the

study, the date and reason for withdrawal will be recorded on the eCRF. If a treatment-related AE is ongoing at the time of withdrawal, the TI will attempt to follow the subject until the AE has been resolved or follow-up is no longer possible. The TI shall ask for the subject's permission to follow his/her status/condition outside the study.

Randomized subjects who withdraw before treatment will not be replaced by another subject. The subject number and associated randomization number of the withdrawn subject will not be reassigned to a different subject.

If a subject fails to return for 1 or more scheduled study visits, the TI (or designee) will attempt to contact the subject to determine and document the reason the subject has failed to return, and to encourage compliance with the study visit schedule.

At regular intervals, the TI (or designee) will record on the eCRF the reasons for which any subjects are discontinued from the study, including subjects who signed the ICF but do not proceed to randomization.

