#### 6.6 Withdrawal Criteria

The subject may withdraw at will at any time.

If a subject has a positive urine pregnancy test at the time of the initial or maintenance treatment visit, the subject will not be eligible for treatment and will be withdrawn from the study. If a subject has a positive urine pregnancy test after treatment, she will continue all scheduled visits and non-treatment procedures. The pregnancy will be followed as described in Section 10.3.

In addition, a subject must be withdrawn from the study if he/she:

- receives any dermal filler or fat injection to the chin area
- undergoes facelift or facial reconstructive surgery
- receives treatment with hyaluronidase in the chin area
- changes his/her decision about having photographs taken

A subject may also be withdrawn at the discretion of physician.

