- Tenderness or pain in the jaw when chewing, which can usually be treated with over-the-counter painkiller and generally resolves within a few days
- Numbness, problems with chewing and mild speech related difficulties which typically resolve without treatment within a few days
- Rare cases of allergy, severe sensitivity, localized inflammation and abscesses
- Very occasionally, delayed side effects can occur many months after the treatment. These delayed side effects may include: lumps, bumps, nodules, cysts, swelling, pain, bruising, skin tightness, and product dislocation.
- In rare circumstances, facial fillers have been injected into blood vessels causing blockage and embolization which can result in skin necrosis, ulceration, or vision changes. Risks to vision include complete blindness, partial blindness, blurred vision, double vision, loss of peripheral vision, loss of a portion of the visual field or anterior segment ischemia (characterized by decreased vision and pain). These effects can be temporary or permanent but are rare.
- In rare circumstances, facial fillers have been associated with granulomas, which are small inflammatory nodules under the skin.
- In rare circumstances, stroke

Unforeseeable risks or results are also a possibility. The risk of developing a serious complication is small. If a complication occurs, subjects will be advised to contact the TI who will use his/her medical judgment to do whatever is necessary to treat the subject. In the event of vision loss, the subject must also be referred to a retinal specialist for evaluation and appropriate care.

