# 11.3 Procedures for Reporting an AE or ADE

All AEs or ADEs occurring during the study period (after signing of the ICF) are to be recorded on the appropriate eCRF.

If a treatment-related AE is ongoing at the time of exit, the TI will attempt to follow the subject until the AE has been resolved or follow-up is no longer possible. The TI shall ask for the subject's permission to follow his/her status/condition outside the study.

The TI will report AESIs to Allergan within 24 hours of awareness of the event by completing an AE eCRF and notifying Allergan study management personnel and the Medical Safety Physician by fax or email. Allergan will notify FDA of any AESI within 10 working days of Allergan's awareness of the event.

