- ! For applicable effectiveness and safety endpoints, baseline is defined as the last non-missing value on or before the latter of randomization date or first treatment date in the control period, unless otherwise specified.
- ! Descriptive statistics for continuous variables include the sample size (N), number of non-missing observations (n), mean, standard deviation, median, 1st and 3rd quartiles, minimum, and maximum. For continuous data, a 2-sample t-test or Wilcoxon rank test will be used for between group comparisons as appropriate, unless stated otherwise. Specified that 95% CI for continuous variables will be based on the standard normal distribution in Section 5.1.
- ! Summary statistics for categorical variables include the sample size (N1), frequency count, and percentage. Ordinal categorical variables will be analyzed using the Cochran-Mantel-Haenszel test. Nominal variables will be analyzed using Pearson's chi-squared test or Fisher's exact test as appropriate. The 95% CI will be computed using the exact binomial method.
- ! The level of significance used for all statistical tests will be 0.05, 2-sided, unless stated otherwise.
- ! The change from baseline values will be computed as the value for the post baseline visit minus the baseline value, unless otherwise indicated.
- ! In the event if any data collected was after exit, it will not be included in tables but will only be presented in the listings.
- ! All statistical analysis will be performed using SAS version 9.3 or higher.
- ! MedDRA 22.1 or newer will be used to code AEs and medical history.
- ! WHO Drug Dictionary 201703 or newer will be used to code medications.

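### Section 6.6 requires study withdrawal of an already injected subject who changes the photograph decision, which ends scheduled safety and questionnaire follow-up that the documents do not tie to a photograph

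*Protocol*

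**What the plan says.** **At entry.** Protocol Section 10.1.1 states: "Subjects choosing not to participate in facial digital imaging through checkbox selection on the ICF will be excluded from the study". It is an entry rule and does not address subjects already treated.

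**After entry.** The mandatory list in Section 6.6 opens with "In addition, a subject must be withdrawn from the study if he/she", and one of its items is that the subject "changes his/her decision about having photographs taken". Nothing separates a change of mind before injection from one after it.

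**Pregnancy, in the same section.** After a positive test following treatment, "she will continue all scheduled visits and non-treatment procedures". A positive test at the initial or maintenance treatment visit leads to withdrawal instead.

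**What remains after withdrawal.** Under Early Discontinuation of Subjects, "Subjects who discontinue early are to complete applicable study visit procedures and Early Exit Visit procedures". The Early Exit columns of Tables 2, 3 and 5 include adverse events and concomitant medications. For a treatment-related event still ongoing at exit, Section 11.3 says that "the TI will attempt to follow the subject until the AE has been resolved or follow-up is no longer possible". Section 11 requires treatment-related serious events ongoing at the final visit to be followed until resolved or stable, and Section 11.4 requires follow-up of every subject with a serious event.

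**Late events.** Section 11.1.1 lists as a known risk: "Very occasionally, delayed side effects can occur many months after the treatment".

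**Analysis.** SAP Section 5.1: "In the event if any data collected was after exit, it will not be included in tables". The sentence goes on to place such data in the listings.

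**The concern.** Refusing images is a good reason not to enter a trial whose primary rating is made from images. It is a weaker reason to stop watching someone who already carries the filler. Section 10.1.1 treats imaging as a separate checkbox on the consent form, so withdrawing that permission is not the same as refusing follow-up. Section 6.6 nevertheless gives it the same result.

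At stake is avoidable loss of safety and subject-reported data on injected subjects, in a trial whose own risk list includes events that appear months later. The loss could also be selective, if a visible lump or a disappointing result makes a subject less willing to be photographed. That is plausible, but the documents contain nothing to confirm it.

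**Working it through.** No single calculation decides this point. The check sets the passages side by side and then bounds the size.

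**1. What depends on a photograph, and what stops at exit**

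| Assessment | Tied to images in the documents? | After the Early Exit Visit |
|---|---|---|
| ALJDS by the evaluating investigator | Yes (SAP 1.2) | Stops; not obtainable without images in any case |
| Query for new adverse events | No | Scheduled query stops; ongoing treatment-related events and serious events are still followed |
| Vision-symptom question at each visit or call (Protocol 6.2) | No | Stops |
| Vision examinations | No | Scheduled only on treatment days and at Day 14 after each treatment; little or nothing left to lose after that |
| Facial sensation (2-point and light touch, Protocol 6.2) | No | Stops; not in the Early Exit columns |
| Jaw Functional Limitation Scale, FACE-Q | No | Stops; not in the Early Exit columns |
| GAIS, investigator and subject | Not stated either way | Stops; not in the Early Exit columns |

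Section 11.2 ends adverse event collection at the last subject visit. Whether that means the subject's own last visit or the last visit in the study, no contact is scheduled for a withdrawn subject after the Early Exit Visit.

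**2. Follow-up time lost**

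Table 3 schedules visits at Months 1, 3, 6, 9 and 12. A VOLUX subject withdrawn after Month 1 loses 12 − 1 = 11 months and 4 of the 5 visits. A control subject withdrawn after Month 1 of delayed treatment loses the Month 3 and 6 visits and the safety telephone calls at Months 9 and 12 described in the Synopsis. Those calls involve no image, so the protocol already follows injected subjects for safety without one.

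**3. Effect on the effectiveness endpoints**

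- Primary: a withdrawn subject with baseline ALJDS on both sides stays in the mITT population (SAP Section 4), and a missing Month 6 ALJDS is imputed from baseline, Month 1 and Month 3 (SAP 5.3.2). The same would apply if the subject stayed without images, so withdrawal gains nothing here.
- FACE-Q at Month 6: the paired test uses observed data only (SAP 5.4.1 and Table 5-5). A subject withdrawn before Month 6 drops out of it but could have contributed by staying. One subject is 1/162 = 0.6% to 1/144 = 0.7% of the randomized VOLUX arm.

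**4. Effect on the stated safety precision**

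Inputs from Protocol Section 8.5: 144 and 48 randomized, with 5% and 15% drop-out before treatment.

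- Treated: 144 × 0.95 = 136.8 and 48 × 0.85 = 40.8. Rounding each down gives 136 + 40 = 176, the plan's figure.
- Chance of at least one event at 1.5% incidence: 1 − 0.985^176 = 0.930, which agrees with the plan's statement of at least 92%.
- If k treated subjects contributed nothing: 1 − 0.985^(176 − k).

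| k lost | Chance of at least one event |
|---|---|
| 0 | 0.930 |
| 5 | 0.925 |
| 10 | 0.919 |
| 18 | 0.908 |

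The documents give no rate of changed photograph decisions. I assume 0 to 5; the larger values are a stress test. All the rows with k above 0 overstate the loss, because events recorded up to exit still count.

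**The case against.** The strongest reply is that this is a legitimate design choice. Images carry the primary endpoint, and Section 10.1.2 requires authorization covering digital images before any study procedure. A subject who withdraws it no longer meets a condition of participation. Pregnancy after treatment leaves every effectiveness measure obtainable and refusing photographs does not, so treating the two differently is not a contradiction. Section 6.6 also withdraws some pregnant subjects, namely those who test positive at the initial or maintenance visit. The number affected is unknown and probably small.

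Most of this stands. The two rules do not conflict, and the pregnancy rule shows only that a route for staying in follow-up already exists in the same section. What the reply does not supply is a reason for ending the non-image assessments. The missing ALJDS explains stopping the ALJDS, and the SAP already handles that missing value. Several other mandatory triggers in Section 6.6 (filler or fat injection, facelift, hyaluronidase) alter the treated area; a photograph decision does not.

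A reader might infer that the subject loses all adverse event, vision and questionnaire follow-up. The documents do not support that. The Early Exit Visit records adverse events, procedures applicable at the exit visit are completed, and ongoing treatment-related events and all serious events are followed. A subject past Day 14 with no further treatment has no vision examination left to miss. Nor does SAP Section 5.1 discard data collected after exit: it lists them, and it does so for every exited subject.

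**Conclusion.** The point holds in a limited form. Section 6.6 makes withdrawal mandatory for an injected subject who changes the photograph decision. After the Early Exit Visit this ends scheduled surveillance for new or delayed events, the vision-symptom question, facial sensation testing and the subject questionnaires, without a stated reason.

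For one subject the loss can be large: up to 11 of 12 months. For the trial it is probably small: with 0 to 5 of 176 treated subjects affected (assumed), the chance of seeing a 1.5% event stays between 0.925 and 0.930, and the handling of the primary endpoint is unchanged. The case rests on keeping safety and subject-reported data on treated subjects at almost no cost. It does not rest on power, or on a claim that refusal is linked to complications, for which the documents offer no evidence.

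**What to change.** Leave the entry rule in Section 10.1.1 as it is. In Section 6.6, replace mandatory withdrawal for a changed photograph decision after treatment with a rule to this effect: imaging and image-based ratings (ALJDS) stop; with the subject's agreement, all other scheduled visits, adverse event queries and non-image assessments continue; the subject leaves the study only on withdrawing consent to follow-up or under another withdrawal criterion.

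The same amendment should say whether the GAIS ratings and the pronunciation video count as image-dependent, because the documents do not settle this. Whether such a subject could receive further study injections is a clinical matter for the sponsor to state; this point takes no position on it.

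The SAP needs no new method. A missing Month 6 ALJDS goes through the multiple imputation in Section 5.3.2, and data from a subject who has not exited go into the tables in the ordinary way. The cost is one amended bullet, with matching consent wording if needed, and a few subjects followed without image-based data.
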